8.8 Serious Adverse Event Recording Period

SAEs will be collected and recorded by the Investigator beginning from the signature of the ICF through the end of the short term follow-up phase.

8.9 Serious Adverse Event Follow-up Period

All subjects who experience SAEs will be followed until the events resolve, stabilize, become chronic or the subjects are lost to follow-up.

8.10 Regulatory Reporting of Adverse Events

If there are serious, unexpected adverse drug reactions (for Europe, SUSAR: Suspected Unexpected Serious Adverse Reaction) associated with the use of the IMP, the appropriate regulatory agency(ies) and all participating investigators will be notified in accordance with the following Guidance for Industry: Clinical Safety Data Management: Definitions and

This document contains confidential information. It is intended solely for the use of the principal investigator, co-investigators, staff, appropriate institutional review boards or ethical committees, and other required regulatory bodies.

Standards for Expedited Reporting (ICH-E2A), Detailed Guidance on the Collection, Verification and Presentation of Adverse Event/Reaction Reports Arising from Clinical Trials on Medicinal Products for Human Use (CT-3). Clinically significant bacteremia and clinical sepsis associated with the use of the IMP will also be reported on an expedited basis.

It is the responsibility of the investigator to promptly notify the Institutional Review Board (IRB)/Independent Ethics Committee (IEC) of all unexpected serious adverse drug reactions involving risk to human subjects. An unexpected event is one that is not reported in the current Investigator's Brochure.

9 DATA MANAGEMENT

A validated clinical data management system will be used for capturing and managing data from the study. Data will be entered into the eCRFs following the eCRF Completion Guidelines. The CRFs for this study will be eCRF.

The Investigator should ensure the accuracy, completeness and timeliness of the data recorded on the eCRFs. Data recorded on the eCRF will be consistent with source documents. Any discrepancies must be explained or resolved.

Completed eCRFs will be reviewed by the Sponsor's monitoring staff or the Sponsor's designee. An eCRF will be completed for each included subject.

After the last subject completes the end of the short term follow-up phase, the database will be locked and the study will be unblinded for the purpose of the statistical analysis. Evaluation of all efficacy, safety, PK and PD endpoints as described in Section 10.1 will occur, except for the overall tumor response to chemoradiation therapy (Safety endpoint 3). This safety endpoint will be evaluated following the second database lock after the last subject completes the long term follow-up phase (i.e. 12 months after the last dose of CRT).

10 STATISTICAL METHODS

Statistical considerations are briefly described below.

More details on the analysis and presentation of study results will be provided in the statistical analysis plan (SAP). The SAP will be finalized prior to the unblinding of treatment allocation codes.

Descriptive statistics will be used to summarize all data collected from this study, with inferential statistics provided for the primary and secondary endpoints. Unless stated

This document contains confidential information. It is intended solely for the use of the principal investigator, co-investigators, staff, appropriate institutional review boards or ethical committees, and other required regulatory bodies.

otherwise, the term "descriptive statistics" refers to number of subjects (n), mean, median, standard deviation (SD), standard error of the mean (SEM), minimum, and maximum for continuous data, and frequency tables with counts and percentages for categorical data. The term "treatment group" refers to the randomly assigned IMP, either AG013 or placebo, each topically applied three times daily.

For change from baseline calculations, "baseline" refers to the last measurement obtained prior to the first dose of IMP. Study days will be defined relative to the Baseline Visit (Day 1 of CRT).

All available assessments of oral mucositis (OM) will be used to derive efficacy endpoints (duration, incidence and onset of OM), including WHO severity grades recorded twice per week during the treatment phase (start of CRT until 14 days after the last CRT dose) and weekly during the short term follow-up period (4 weeks after the end of CRT) to capture resolution of OM, as required.

Adjustment for multiple significance testing will be performed using a hierarchical closed testing procedure to control the overall Type 1 error rate at 5%. If the primary efficacy endpoint demonstrates a statistically significant treatment effect (two-sided $p \le 0.05$), secondary efficacy endpoints will be tested sequentially at the same level 0.05 in a prespecified order (as listed below). The process continues until the first time the p-value exceeds 0.05, at which point testing stops and no further significance may be claimed.

Tabulations of summary statistics, graphical presentations, and statistical analyses will be performed using SAS[®] Software (Version 9.3 or higher).

10.1 Study Endpoints

10.1.1 Primary Efficacy Endpoints

1. Duration (in days) of severe oral mucositis (WHO grades 3 or 4)

10.1.2 Key Secondary Efficacy Endpoints (hierarchical)

- 1. Time to onset of severe oral mucositis (WHO grades 3 or 4)
- 2. Incidence of severe oral mucositis (WHO grades 3 and 4)
- 3. Duration of ulcerative oral mucositis (WHO grades 2, 3 or 4)
- 4. Time to onset of ulcerative oral mucositis (WHO grades 2, 3 or 4)
- 5. Incidence of ulcerative oral mucositis (WHO grades 2, 3 or 4)

This document contains confidential information. It is intended solely for the use of the principal investigator, co-investigators, staff, appropriate institutional review boards or ethical committees, and other required regulatory bodies.

10.1.3 Safety Endpoints

- 1. Incidence of adverse events, including serious adverse events (SAEs) and clinically significant laboratory abnormalities
- 2. Changes in vital signs and clinical laboratory parameters
- 3. Overall tumor response to chemoradiation therapy (during 12 months following the last dose of CRT).

10.1.4 Secondary Efficacy Endpoints

- 1. Cumulative radiation dose to development of severe oral mucositis (WHO grades 3 or 4) and ulcerative oral mucositis (WHO grades 2-4)
- 2. Patient-reported pain as measured by Question 2 (mouth and throat soreness) of the Oral Mucositis Daily Questionnaire
- 3. Use of analgesics to control oral pain (number and percentage of subjects using per type)

10.1.5 Pharmacokinetic (PK) and Pharmacodynamic (PD) Endpoints

- 1. Assessment of biomarkers (primarily pro- and anti-inflammatory cytokines)
- 2. PK profile of AG013 based on blood/serum samples and buccal smears in a subset of subjects (15 subjects on AG013 and 15 subjects on placebo, in up to 10 sites).

10.1.6 Exploratory Efficacy Endpoints for OM (linked to primary endpoint)

- 1. Incidence of severe mucositis (WHO grades 3 or 4) within subgroups defined by cumulative radiation doses of 30 Gy, 40 Gy, 50 Gy and 60 Gy
- 2. The AUC of an OM severity-time curve
- 3. Mucositis severity parameters (incidence, duration, time to onset of grades 3,4 and 2,3,4) based on NCI-CTCAE v4.0 and RTOG criteria

10.1.7 Other Exploratory Endpoints

- 1. Genomic differentiation of AG013 responders and non-responders
- 2. Frequency and duration of RT interruptions
- 3. Healthcare resource use including: unplanned office visits, ER visits, hospitalizations, and non-prophylactic gastrostomy tube placement (US sites only)

This document contains confidential information. It is intended solely for the use of the principal investigator, co-investigators, staff, appropriate institutional review boards or ethical committees, and other required regulatory bodies.

4. Comparison of AG013 efficacy in OM in patients with HPV negative versus HPV positive tumors

10.2 Sample Size Consideration

A sample size of 160 evaluable subjects (80 per group) will provide approximately 80% power to detect a 5-day difference between groups in the average number of days with severe OM (WHO grade 3 or 4) at the two-sided 5% significance level; this calculation is based on Student's t-test and assumes the standard deviation for duration of severe OM is 10.8 days. To be evaluable, subjects must receive at least 4 weeks of IMP and a cumulative radiation dose of 50Gy. Additional subjects will be enrolled to account for non-evaluability. The primary analysis method (Cochran-Mantel-Haenszel test), though different from the t-test approach, will have higher power since the stratified analysis is expected to be more efficient.

Note that 160 subjects will also afford approximately 85% power to detect a 25% difference in the incidence of severe OM (WHO grades 3 or 4), assuming that the incidence is reduced from 75% in the placebo group to 50% in the AG013 group; this calculation is based on a Fisher's Exact test at the two-sided 5% significance level.

10.3 Definitions of Study Populations for Analysis

10.3.1 The Safety (SAF) Analysis Set

All subjects who are randomized to treatment and receive at least one dose of IMP will be included in the safety (SAF) analysis set.

Subjects in this population will be analyzed according to the treatment they actually receive. The SAF population will be used as the basis for all safety analyses, as well as summaries of demographic and baseline data, concomitant medications, and IMP exposure/compliance and tolerability data.

10.3.2 Intent-to-Treat (ITT) Population

The ITT population will include all randomized subjects. Subjects will be analyzed according to the treatment group to which they are randomized, regardless of treatment actually received. This population will serve as the basis for the primary efficacy analysis.

A modified ITT (mITT) population, defined as all ITT subjects who receive IMP and have postbaseline efficacy data, will be used for all primary and secondary efficacy endpoints.

10.3.3 The Per Protocol (PP) Population

The PP population will consist of all mITT subjects who receive a minimum of 4 weeks of IMP and a cumulative radiation dose of 50Gy to oral and oropharyngeal sites at risk; any other criteria for excluding subjects from this analysis set must be defined in the SAP and finalized

This document contains confidential information. It is intended solely for the use of the principal investigator, co-investigators, staff, appropriate institutional review boards or ethical committees, and other required regulatory bodies.

prior to unblinding the database. This population will be used for supportive efficacy analyses.

10.3.4 The Pharmacokinetic (PK) and Pharmacodynamic (PD) Analysis Sets

Subjects who receive the IMP as scheduled and provide sufficient samples to reliably estimate the PK parameters will be included in the PK analysis set. Subjects in this population will be analyzed according to the treatment they receive.

The PD analysis set will include all subjects with biomarkers evaluated at baseline and at least once after the start of IMP. The PD analysis will be performed only after an efficacy signal is determined.

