2 OBJECTIVES

Primary Objectives

Primary Efficacy Objectives:

• To evaluate the efficacy of topically administered AG013 compared to placebo for reducing OM in patients undergoing chemoradiation for the treatment of head and neck cancer, as measured by the duration, time to development, and overall incidence of OM during the active treatment phase, beginning from the start of chemoradiation therapy (CRT) until 2 weeks following its completion.

Primary Safety Objectives:

• To determine the safety and tolerability of AG013 during the active treatment phase described above.

This document contains confidential information. It is intended solely for the use of the principal investigator, co-investigators, staff, appropriate institutional review boards or ethical committees, and other required regulatory bodies.

Secondary Objectives

Secondary Efficacy Objectives:

• To evaluate the effect of AG013 on patient-reported symptoms and analgesic use during the active treatment phase, and on the cumulative radiation dose administered before the onset of OM.

Secondary Pharmacokinetics and Pharmacodynamic Objectives:

• To assess biomarkers and, in a subset of subjects, the PK profile of AG013.

Exploratory Objectives

Exploratory Efficacy Objectives for OM

• Exploratory objective for OM Severity linked to time, duration and incidence of OM (linked to Primary Efficacy Objectives)

Other Exploratory Objectives:

- To investigate the genomic differentiation of AG013 responders and non-responders.
- To compare the efficacy of AG013 in patients with human papilloma virus (HPV) negative tumors versus HPV positive tumors.
- To evaluate the effect of AG013 on healthcare resource utilization (US sites only).
- To compare the frequency and duration of RT interruptions.

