Subjects will undergo study assessments twice a week during the active treatment phase. Subjects will be evaluated two times per week for adverse events (AEs) and for the presence and severity of OM throughout CRT. The presence and severity of OM will be determined by trained observers using the World Health Organization (WHO) OM toxicity scale.

Subjects will complete a study diary daily starting the first day of radiation therapy and continuing through to the end of the active treatment phase of the study. Patients with WHO persistent grade mucositis of 2 or greater at the end of the active treatment phase will continue to complete the daily diaries until mucositis decreases to grade of 0 or 1. The diary contains the Oral Mucositis Daily Questionnaire (OMDQ), a record of analgesic medication use, and questions regarding IMP dosing, tolerability general quality of life. The diary will be reviewed by study staff at each study assessment time point in order to ensure complete and accurate data collection.

This document contains confidential information. It is intended solely for the use of the principal investigator, co-investigators, staff, appropriate institutional review boards or ethical committees, and other required regulatory bodies.

Short Term Follow-up: Short term follow-up will begin after the completion of the active treatment phase (Day 15 Post CRT) and will continue for four weeks (Day 42 Post CRT (\pm 3 Days)). During short term follow-up, patients will be assessed weekly for adverse events and mucositis severity. Patients with WHO persistent grade mucositis of 2 or greater at the end of the short term follow-up phase will continue to be followed weekly until mucositis decreases to grade of 0 or 1.

Long Term Follow-up: Tumor status will be assessed at 3, 6 and 12 months (+/- 14 days) following the last dose of CRT.

Blood samples for biomarkers studies will be collected at specific time points in all subjects. Blood and buccal smears will be collected at specific time points in a subset of subjects who consent separately. These will be used to evaluate the pharmacokinetics (PK) of AG013. Additional blood samples for genetic responder/non-responder studies will be collected at specific time points for subjects who consent separately.

The total amount of blood taken for the whole study is maximum 300 ml. The blood sampling includes the following:

- 1. 11 samples of 15 ml each for routine laboratory testing

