12.10 Study Report

The Principal Investigator will submit to the Sponsor a copy of the report issued to the IRB/IEC. A full study report will be written after completion of the statistical analysis including the evaluation of the efficacy, safety, PK and PD endpoints as described in Section 10.1. The overall tumor response to chemoradiation therapy (Safety endpoint 3) and

This document contains confidential information. It is intended solely for the use of the principal investigator, co-investigators, staff, appropriate institutional review boards or ethical committees, and other required regulatory bodies.

updated safety information will be described in an addendum to the study report after the second database lock at the end of the study.

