7.6 THE PHARMACODYNAMIC (PD) ANALYSIS SET

The PD analysis set will be described in a separate analysis plan, since the assessment of biomarkers (primarily pro- and anti-inflammatory cytokines) is an optional analysis to be performed only in case of a positive outcome of the study.

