8.9 OTHER ENDPOINTS AND ANALYSIS

8.9.1 PHARMACOKINETICS, PHARMACODYNAMICS AND GENOMICS

The PK analysis will be performed at Precigen ActoBio (formerly Intrexon Actobiotics), and individual outcomes per patient per visit will be derived. PK parameters will be calculated by summarizing the parameters and concentrations by visit. Analysis will be descriptive, no hypothesis testing will be performed. Listings for PK data will be created as well.

Blood and buccal smears will be collected at specific time points in a subset of subjects who consent separately (targeting 15 subjects on AG013 and 15 subjects on placebo). Descriptive summary statistics will be used to evaluate the pharmacokinetics of AG013 by treatment group and study visit. Blood levels of AG013-sAGX0085 bacteria, serum levels of hTFF1 and buccal mucosa levels of AG013 (both AG013-sAGX0085 bacteria and hTFF1) will be summarized using descriptive statistics, including graphical methods.

Biomarker assessments will be listed and summarized for each treatment group by time point using descriptive statistics (mean, median, SD, SEM, coefficient of variation, minimum, and maximum) and graphical displays. The relationship between biomarkers and efficacy outcomes will be explored via correlation analysis, as appropriate. Note: this analysis will only be performed in case of a positive outcome on the study regarding the efficacy outcome, i.e. positive primary endpoint.

PD (biomarker) and Genomic analyses will be described in a separate plan.

Note: PD (biomarker) and Genomic analyses will only be performed in case of a positive efficacy outcome on the study.

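### The plan contradicts itself on whether biomarkers, a secondary objective, are analysed whatever the efficacy result, and it leaves the biomarker analysis set and plan in an undated document for work that follows unblinding

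*Protocol*

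**What the plan says.** **Status and sampling.** Protocol Section 2 gives the secondary PK/PD objective as "To assess biomarkers and, in a subset of subjects, the PK profile of AG013". Protocol Section 3 adds: "Blood samples for biomarkers studies will be collected at specific time points in all subjects".

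**Unconditional statements.** For the first database lock, Protocol Section 9 says: "Evaluation of all efficacy, safety, PK and PD endpoints as described in Section 10.1 will occur". Its only exception is tumor response. Protocol 12.10 describes a full study report "including the evaluation of the efficacy, safety, PK and PD endpoints as described in Section 10.1", with tumor response and updated safety left to an addendum.

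**Conditional statements.** Protocol 10.3.4 says: "The PD analysis will be performed only after an efficacy signal is determined". SAP 5.5 calls the PD endpoints optional and ties them, as does SAP 7.6, to the study turning out positive. SAP 8.1 and 8.9.1 refer in places to a favourable efficacy result and in others to success on the primary endpoint. SAP 5.7 applies the primary-endpoint form to genomics.

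**Analysis set and plan.** Protocol 10.3.4 fixes the set: "The PD analysis set will include all subjects with biomarkers evaluated at baseline and at least once after the start of IMP". SAP 7.6 instead says: "The PD analysis set will be described in a separate analysis plan". SAP 8.9.1 says: "PD (biomarker) and Genomic analyses will be described in a separate plan". No date is given for that plan. SAP 8.1 unblinds at the first lock and puts PD and genomic evaluation later.

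**Declared deviations.** SAP 9 lists three: baseline summaries also for ITT, shift tables in place of laboratory summaries, and no imputation of severe scores in the incidence analyses.

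**The concern.** Protocol Sections 9, 10.3.4 and 12.10 cannot all be followed. After a negative trial, two of them require the biomarker results and one withholds them. A secondary objective that is reported only when the primary succeeds is reported selectively. It is also withheld in the case where it would tell most, because after a negative result the biomarkers help separate no biological effect from one too small to show clinically.

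The second issue is timing. Protocol Section 10 requires the SAP to be final before the treatment codes are opened. Nothing extends that requirement to the separate PD and genomic plan, and the analyses it governs come after unblinding and only after a favourable result. What it leaves open could therefore be settled by people who already know efficacy by arm.

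**Working it through.** The point rests on text, so the places are compared first. The arithmetic only illustrates how often the condition would fail.

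**1. Is PD analysis conditional?**

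| Place | Condition on PD |
|---|---|
| Protocol 9 | none; first lock; only tumor response excepted |
| Protocol 12.10 | none; in the full study report |
| Protocol 10.3.4 | an efficacy signal, not defined |
| SAP 5.5, 7.6 | study positive |
| SAP 8.1 | efficacy positive; elsewhere in the section, primary endpoint positive |
| SAP 8.9.1 | primary endpoint positive; closing note, efficacy positive |

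The choice of wording matters. SAP 8.7.1 runs the primary analysis in ITT, mITT and PP. A result that misses in ITT but reaches significance in mITT, or a missed primary with a favourable key secondary, might count as a signal under the protocol's term and not under the strictest SAP wording.

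**2. What is fixed and what is open?**
- Fixed: sampling at baseline, weeks 3 and 5, last RT day, last IMP day and four weeks after RT (Protocol 6.3.4 and Appendix D).
- Fixed: descriptive summaries by arm and time point, graphs, and correlation with efficacy where appropriate (Protocol 10.7, SAP 8.9.1).
- Fixed in the protocol but not carried into the SAP: the PD set.
- Open: which cytokines, and how the correlation is done.

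**3. What changed without being listed in SAP 9?**
- The PD set is deferred (Protocol 10.3.4 against SAP 7.6).
- PD evaluation moves from the first lock to later (Protocol 9 against SAP 8.1).
- Genomics becomes conditional (Protocol 10.1.7 and 10.5 against SAP 5.7, 8.1 and 8.9.1).

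**4. Illustration: how often would the objective go unanswered?**

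Inputs from Protocol 10.2: difference 5 days, SD 10.8, 80 evaluable per group, two-sided 5%, Student's t-test. Protocol 4.1 gives about 200 enrolled, so about 100 per arm in ITT. The condition is read as a significant primary result favouring AG013.

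- The plan's own figure: it states approximately 80% power. The noncentral t calculation with 80 per group gives 82.9%, so the stated figure is slightly conservative.
- Formula (normal approximation): SE = SD × √(2/n); P(unanswered) = 1 − P(Z > 1.96 − difference/SE).
- 80 per arm: SE = 10.8 × √(2/80) = 1.708 and 5/1.708 = 2.93. P(Z > −0.97) = 0.833, so 16.7% unanswered. By the t-test, 100 − 82.9 = 17.1%.
- 100 per arm: SE = 10.8 × √(2/100) = 1.527 and 5/1.527 = 3.27. P(Z > −1.31) = 0.906, so 9.4% unanswered. By the t-test, power is 90.3%, so 9.7%.
- No effect, any n: 1 − 0.025 = 97.5% unanswered.
- Smaller true effects with 80 per arm: 78.5% unanswered at 2 days and 58% at 3 days.

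The samples at issue number at most 6 per subject (Protocol Section 3) × about 200 subjects = about 1,200.

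**The case against.** **The trigger is effectively defined.** SAP 8.9.1 equates a positive efficacy outcome with a positive primary endpoint. Protocol Section 10 sets two-sided p ≤ 0.05 for that endpoint, and Protocol 10.5 and SAP 8.7.1 designate ITT as primary. This largely stands: a reader might infer that the trigger is undefined throughout, but that is true only of the protocol's term. The SAP's fault is inconsistent wording, and a reader still has to assemble direction, p-value and population from other sections.

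**The condition was already in the protocol.** This stands. Making PD conditional is in Protocol 10.3.4, so it is not itself an undeclared SAP deviation. The three items in step 3 of the working are.

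**Methods exist.** This stands for descriptive summaries and sampling times. A reader might infer that the whole PD analysis is unspecified, or that time points can be picked at will, and the documents contradict both. SAP 7.6 also names no competing set; it leaves open what the protocol had closed.

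**Silence is not permission.** The documents do not say the separate plan will be written after unblinding. They only fail to require that it be written before. That supports asking for a date, not asserting misuse.

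**The impact is low.** PD is descriptive and outside the hierarchical tests. A reader might infer a threat to the type I error of the primary or key secondary endpoints, but no between-arm biomarker test is planned and nothing in the hierarchy depends on PD. Holding cytokine assays until efficacy is seen is also a defensible use of resources in Phase 2. That defends the conditional option, but not its conflict with Protocol 9 and 12.10 or with secondary-objective status.

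**Conclusion.** The point holds as a contradiction and a timing gap. Protocol 9 and 12.10 promise PD evaluation and reporting without condition, while Protocol 10.3.4 and the SAP make it depend on a favourable efficacy result under several wordings. The SAP reopens the PD set and defers it, with the PD and genomic plan, to an undated document for work done after unblinding. The cytokine list and correlation method could then be chosen with efficacy by arm known.

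The consequence is selective reporting of a secondary objective and possible outcome-driven specification. It does not reach the primary or key secondary conclusions. The frequencies (about 17% unanswered at the planned effect with 80 per arm, about 10% with 100 per arm, 97.5% at no effect) are illustrations. They read the condition as a significant primary result favouring AG013 and use a t-test in place of the stratified CMH test. The 100-per-arm figure also assumes the same 5-day effect and SD in all randomized subjects; dilution by non-evaluable subjects would raise it. None of these figures measures the effect of choosing methods after unblinding, which the documents give no basis to quantify.

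**What to change.** 1. Put the PD set of Protocol 10.3.4 back into SAP 7.6.
2. Finalise and date the PD and genomic plan, with named cytokines and the correlation method, before the first database lock and unblinding.
3. Use one rule in Protocol 9, 10.3.4 and 12.10 and in SAP 5.5, 5.7, 7.6, 8.1 and 8.9.1. Either summarise biomarkers whatever the primary result, or keep a single trigger (primary ITT CMH test, two-sided p ≤ 0.05, favouring AG013) and relabel biomarkers as a conditional exploratory objective.
4. List the PD-set deferral (if any of it remains), the later PD timing and the condition on genomics in SAP 9.

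The cost is wording changes and writing the separate plan earlier. Added assay cost arises only under the unconditional option.
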